9.5 Safety and Tolerability Assessments

9.5.1 Adverse events

Where changes in severity are recorded in the Case Report Form (CRF), each separate severity of the adverse event (AE) will be reported in the listings, only the most severe will be used in the summary tables. A pre-existing condition is defined as an AE that starts before the subject has provided written informed consent and is ongoing at consent. A non-treatment emergent AE is defined as an AE which starts after informed consent but prior to dosing. A treatment-emergent AE is defined as an AE which occurs postdose or which is present prior to dosing and becomes more severe postdose.

All AEs will be listed. Treatment-emergent AEs will be summarized by treatment, severity and relationship to the study drug. The frequency (the number of AEs, the number of subjects experiencing an AE and the percentage of subjects experiencing an AE) of treatment-emergent AEs will be summarized by treatment, Medical Dictionary for Regulatory Activities (MedDRA) version 20.0 system organ class and preferred term. The summary and frequency AE tables will be presented for all causalities and those considered related to the study drug. Any serious AEs will be tabulated.

9.5.2 Concomitant medication

Concomitant medication will be coded using the WHO drug dictionary (Version March 2017). Concomitant medication will be listed.

9.5.3 Clinical laboratory parameters

All clinical chemistry, hematology and urinalysis data will be listed. Additionally clinical chemistry, hematology and urinalysis data outside the reference ranges will be listed.

Values for any clinical chemistry, hematology and urinalysis values outside the reference ranges will be flagged on the individual subject data listings.

9.5.4 Vital signs

Vital signs data will be listed for individual subjects.

9.5.5 Electrocardiogram (ECG)

The ECG data will be listed for individual subjects.

9.5.6 Hepatic Monitoring

If a subject experiences elevated alanine aminotransferase (ALT) $\geq 3 \times$ upper limit of normal (ULN), alkaline phosphatase (ALP) $\geq 2 \times$ ULN, or elevated total bilirubin (TBL) $\geq 2 \times$ ULN, liver tests will be performed to confirm the abnormality.

The subjects' liver disease history and associated person liver disease history data will be listed. Any concomitant medication of acetaminophen/paracetamol will be listed. Results from any hepatic monitoring procedures, such as a magnetic resonance elastography (MRE) scan, and a biopsy assessment will be listed, if performed.

Hepatic risk factor assessment data will be listed. Liver related signs and symptoms data will be summarized by treatment and listed. Alcohol and recreational drug use data will also be listed.

All hepatic chemistry, hematology, coagulation, and serology data will be listed. Values outside the reference ranges will be flagged on the individual subject data listings.

9.5.7 Blood Glucose Monitoring and Hypoglycemia

Hypoglycemic events will be appropriately recorded in the CRF. In the case of a hypoglycemic event, the actual blood glucose value, if measured, will be recorded in the CRF, together with any treatments administered. Each category of hypoglycemic events (defined below) will be listed and summarized by treatment.

Hypoglycemia is defined as follows:

- **Documented Glucose Alert Level (Level 1), Plasma Glucose (PG) ≤ 70 mg/dL (3.9 mmol/L):**
 - **Symptomatic hypoglycemia:** an event during which typical symptoms of hypoglycemia are accompanied by PG ≤ 70 mg/dL (3.9 mmol/L)
 - **Asymptomatic hypoglycemia:** an event not accompanied by typical symptoms of hypoglycemia but with PG ≤ 70 mg/dL (3.9 mmol/L)
 - **Unspecified hypoglycemia:** an event during which PG ≤ 70 mg/dL (3.9 mmol/L) but no information relative to symptoms of hypoglycemia was recorded
- **Documented Clinically Significant Hypoglycemia (Level 2) PG < 54 mg/dL (3.0 mmol/L):**
 - **Symptomatic hypoglycemia:** an event during which typical symptoms of hypoglycemia are accompanied by PG < 54 mg/dL (3.0 mmol/L)
 - **Asymptomatic hypoglycemia:** an event not accompanied by typical symptoms of hypoglycemia but with PG < 54 mg/dL (3.0 mmol/L)
 - **Unspecified hypoglycemia:** an event during which PG < 54 mg/dL (3.0 mmol/L) but no information relative to symptoms of hypoglycemia was recorded
- **Severe hypoglycemia (Level 3):** an event requiring assistance of another person to actively administer carbohydrate, glucagon, or other resuscitative actions. During these episodes, the patient has an altered mental status and cannot assist in their care, is semiconscious or unconscious, or experienced coma with or without seizures and may

require parenteral therapy. PG measurements may not be available during such an event, but neurological recovery attributable to the restoration of blood glucose concentration to normal is considered sufficient evidence that the event was induced by a low PG concentration (PG \leq 70 mg/dL [3.9 mmol/L])

- **Severe hypoglycemia requiring medical attention:** a severe hypoglycemic event when patients require therapy by HCPs (EMTs, emergency room personnel, etc)

Other Hypoglycemia:

- **Nocturnal hypoglycemia:** any hypoglycemic event (documented symptomatic, asymptomatic, probable symptomatic, or severe hypoglycaemia) that occurs between bedtime and waking
- **Relative hypoglycemia:** an event during which typical symptoms of hypoglycemia, which do not require the assistance of another person, are accompanied by PG $>$ 70 mg/dL (3.9 mmol/L), but these levels may be quickly approaching the 70 mg/dL (3.9 mmol/L) threshold
- **Overall (or total) hypoglycemia:** This optional category combines all cases of hypoglycemia. If an event of hypoglycemia falls into multiple subcategories, the event is counted only once in this category
- **Probable symptomatic hypoglycemia:** An event during which symptoms of hypoglycemia are not accompanied by a PG measurement but that was presumably caused by a blood glucose concentration \leq 70 mg/dL (3.9 mmol/L).

9.5.8 Injection Site Local Tolerability Assessment Data

Injection-site assessment data will be listed and summarized in frequency tables by treatment and timepoint.

9.5.9 Immunogenicity

The frequency of antibody formation to insulin lispro will be summarized by treatment and listed for individual subjects.

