Pregnancy test/urine drug screen/alcohol breath test	X	X		X	Pregnancy test for female subjects of childbearing potential only. Serum pregnancy test at screening. Urine pregnancy test for all other visits. Alcohol breath test and drug screen may be omitted at follow up.
Study drug administration			0 minute		Time of study drug administration = 0 minute. Study drug will be administered at about the same time on Day 1 of each study period.
Injection-site assessments			0, 60, 240, and 600 minutes		Assessment times are relative to study drug administration time (time 0). The 0-minute assessment will start as soon as practicably possible (within 1 minute) following the injection.
Insulin lispro PK sampling			0, 5, 10, 15, 20, 25, 30, 35, 40, 50, 60, 70, 90, 120, 150, 180, 210, 240, 300, 360, 420, 480, 540, and 600 minutes		Sampling times are relative to study drug administration time (time 0). The 0-minute sample should be taken within 2 minutes prior to planned dosing.

Procedures	Screening	Euglycaemic Clamp Procedure Periods 1 to 6		FU/ ED ^a	Comments
	Up to Day -28	Day -1	Day 1		
Euglycaemic clamp and blood glucose sampling for procedure			The clamp device will automatically sample blood at a rate of 2 mL/h after connection and record a blood glucose value every minute during the clamp procedure. A manual blood sample will also be taken at least every 30 minutes during the clamp for checking the correct functioning of the clamp device blood glucose readings and for safety.		Blood glucose monitoring will be done every minute starting from calibration after connection to the clamp device, baseline glucose establishment, drug dosing, and clamp up to 10 hours after dosing
C-peptide sampling			0, 60, 120, 240, 360, 480, and 600 minutes		Sampling times are relative to study drug administration (time 0). The 0-minute sample should be taken within 2 minutes prior to planned dosing.
Pharmacogenetic sample		X			Period 1 only.
Immunogenicity sample ^b			Pre-dose for Period 1, Period 3, and Period 5	X	Additional samples may be collected if the investigator considers there is a possibility that an adverse event is immunologically indicated.
Discharge from CRU			X		After completion of all study procedures and medical assessment on Day 1. Investigator's discretion to discharge on Day 2.

Abbreviations: CRU = clinical research unit; ECG = electrocardiogram; ED = early discontinuation; FU = follow-up; PK = pharmacokinetics.

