^a Procedures should be performed at least 14 days after the last dose of study drug.

^b Pre-dose assessments, procedures, and sampling may be performed any time before actual dosing on Day 1.

Note: The site should schedule activities as appropriate. In cases when several study procedures are scheduled at the same time, the order of priority will be as follows: PK samples, glucose samples, injection-site assessments, vital signs, ECG, clinical laboratory samples, immunogenicity, C-peptide, and pharmacogenetic samples. If the investigator decides based on clinical judgement not to dose a subject on a given day (for example, because of low blood glucose), the subject's visit may be rescheduled; any procedures performed in that period may be repeated.

3. Introduction

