7.8. Treatment after the End of the Study

Not applicable.

8. Discontinuation Criteria

Subjects discontinuing the study drug and/or study prematurely for any reason should complete AE and other follow-up procedures per Section 2 of this protocol.

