10.3.5. Evaluation of Immunogenicity

The frequency of antibody formation to insulin lispro will be determined. The relationship between the presence (or absence) of antibodies and AEs may be assessed. Likewise, the relationship between the presence of antibodies and the PK parameters and GD response to insulin lispro may be assessed.

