Appendix 5. Blood Sampling Summary

This table summarises the approximate number of venipunctures and blood volumes for all blood sampling (screening, safety laboratories, and bioanalytical assays) during the study.

Protocol I8B-MC-ITSH Sampling Summary

Purpose	Blood Volume per Sample (mL)	Number of Blood Samples	Total Volume (mL)
Screening tests ^a	10	1	10
Clinical laboratory tests ^a	7	2	14
Pharmacokinetic samples serum insulin lispro	1	24 samples × 6 periods = 144	144
Clamp device sampling for glucose ^b	NA	NA	138
Blood glucose during clamp period (Super GL) ^c	0.3	276	82.8
C-peptide	2	7 samples × 6 periods = 42	84
Immunogenicity	5	4	20
Pharmacogenetics	10	1	10
Total for clinical purposes			502.8
Total for clinical purposes rounded up to the nearest 10 mL			510

^a Additional samples may be drawn if needed for safety purposes.

^b Clamp device sampling: 30- to 60-minute calibration, 30-minute baseline plus 10-hour clamp = 11.5 hours × 6 periods = 69 hours × 2 mL/hour = 138 mL.

^c Blood glucose during clamp period (Super GL): 30- to 60-minute calibration, 30-minute baseline plus 10-hour clamp = 11.5 hours × 6 periods = 69 hours × up to 4 samples/hour = 276 blood samples × 0.3 mL/blood sample = 82.8 mL.

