5. STUDY DESIGN

This is a Phase 1, randomised, subject- and investigator-blind, 6-period complete crossover study in up to 42 healthy subjects to evaluate the PK and GD characteristics across a range of LY900014 doses.

Approximately 34 subjects are expected to complete the study. Each subject will be randomised to 1 of 6 treatment sequences comprising single SC doses of 7, 15, and 30 U of LY900014 or Humalog administered SC in the abdominal wall (Table 1). A minimum of 3 days between study dosing of each consecutive study period will be required for an individual subject. Figure 1 illustrates the study design.

Study governance considerations are described in detail in Appendix 3 of the protocol.

Figure 1. Illustration of Study Design

[figure not shown]

Table 1. Treatment Sequence Example

Treatment Sequence	Period 1	Period 2	Period 3	Period 4	Period 5	Period 6
1	LY 7 U	LY 15 U	H 30 U	LY 30 U	H 15 U	H 7 U
2	LY 15 U	LY 30 U	LY 7 U	H 7 U	H 30 U	H 15 U
3	LY 30 U	H 7 U	LY 15 U	H 15 U	LY 7 U	H 30 U
4	H 7 U	H 15 U	LY 30 U	H 30 U	LY 15 U	LY 7 U
5	H 15 U	H 30 U	H 7 U	LY 7 U	LY 30 U	LY 15 U
6	H 30 U	LY 7 U	H 15 U	LY 15 U	H 7 U	LY 30 U

Abbreviations: H = Humalog; LY = LY900014.

Note: this is only an example table for illustrative purpose; subjects will be assigned a treatment sequence according to the actual treatment randomisation schedule provided to the unblinded site pharmacist.

Subjects will be admitted to the clinical research unit (CRU) on the evening before each dosing day and will remain in the CRU for the duration of the clamp period and until discharge by the investigator. Subjects are expected to fast for at least 8 hours before each dose. Following dose administration, each subject will undergo an euglycaemic clamp procedure of up to 10 hours. Upon completion of the clamp procedures, the subjects will be provided a meal and discharged from the CRU in the evening after medical assessments. Subjects may remain in the CRU if deemed necessary for safety monitoring, as determined by the investigator.

Subjects will be required to attend the CRU on at least 8 occasions:

- screening visit (up to 28 days prior to dosing)
- six treatment visits for the dosing and clamp procedure (study Periods 1 to 6) with a minimum period of at least 3 days between consecutive clamp visits
- follow-up visit (at least 14 days after the last dose), or early discontinuation

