6. TREATMENTS

The following is a list of the study treatment abbreviations that will be used in the TFLs.

Study Treatment Name	Treatment order in TFL
7 U LY900014 SC	1
15 U LY900014 SC	2
30 U LY900014 SC	3
7 U Humalog SC	4
15 U Humalog SC	5
30 U Humalog SC	6

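### SAP 9.5.9 tabulates antibody frequency by treatment, but a completer's scheduled samples follow 0, 2, 4 and 6 of the six treatments, so none belongs to one treatment

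*SAP*

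**What the plan says.** SAP 9.5.9 consists of one sentence: "The frequency of antibody formation to insulin lispro will be summarized by treatment and listed for individual subjects". It gives no time point, baseline or rule for attaching a sample to a treatment. SAP section 6 introduces its treatment list with "The following is a list of the study treatment abbreviations that will be used in the TFLs" and names six entries: LY900014 at 7, 15 and 30 U and Humalog at 7, 15 and 30 U.

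The immunogenicity row of the Schedule of Activities (Protocol section 2) reads "Pre-dose for Period 1, Period 3, and Period 5", with a further sample marked in the follow-up/early-discontinuation column. The footnote to that column says "Procedures should be performed at least 14 days after the last dose of study drug". Protocol section 8 sends early leavers to the same visit: "Subjects discontinuing the study drug and/or study prematurely for any reason should complete AE and other follow-up procedures per Section 2 of this protocol". Protocol 9.6.1 also allows extra samples when an adverse event may be immune-mediated.

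Protocol 10.3.5 does not ask for a split by treatment. It says "The frequency of antibody formation to insulin lispro will be determined". The split appears only in the SAP, and SAP section 11 does not list it as a change.

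**The concern.** A by-treatment summary is sound when the measurement is taken within the period in which that treatment was given. That is so for the neighbouring SAP items: injection-site assessments and C-peptide are both collected from 0 to 600 minutes after each dose. Antibodies are sampled differently, before every second dose and then at the end. Each post-dose sample therefore reflects whatever has accumulated over several treatments.

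Exploring antibody formation is exploratory objective 1, and this table is its only planned summary. As the SAP stands, the programmer must invent an attribution rule. The study report could then show antibody frequencies side by side for LY900014 and Humalog, or for the three doses, when the sampling cannot support such a comparison.

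**Working it through.** **Number of samples.** Three pre-dose samples (Periods 1, 3, 5) plus one at follow-up make 4. At 5 mL each, 4 × 5 = 20 mL. This reproduces the immunogenicity row of Protocol Appendix 5, "Immunogenicity 5 4 20" (volume per sample, number, total).

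**Treatments received before each sample.** A sample taken pre-dose in Period k follows k − 1 doses. In a complete crossover every period gives a different treatment, so k − 1 doses means k − 1 different treatments. This holds for any set of sequences.

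| Sample | Treatments already received (completer) |
|---|---|
| Period 1 pre-dose | 1 − 1 = 0 |
| Period 3 pre-dose | 3 − 1 = 2 |
| Period 5 pre-dose | 5 − 1 = 4 |
| Follow-up | 6 |

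**Size at the planned number of completers.** Assume 34 completers and no missing samples.

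- Scheduled samples: 34 × 4 = 136.
- Before any drug: 34 × 1 = 34.
- After dosing: 34 × 3 = 102, of which 0 follow exactly one treatment.
- Each completer supplies 3 post-dose samples for 6 treatment rows.

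**Would a labelling rule help?**

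- *Current-period label.* The sample is drawn before that period's dose and each treatment is given once, so the label always names a treatment the subject has not yet had. Follow-up has no current period.
- *Last-dose label.* Two doses are given between consecutive samples (1–2, 3–4, 5–6). The last dose cannot be separated from the one before it, or from earlier exposure.

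**If treatment meant product only.** This depends on the sequences. SAP Table 1 is marked as illustrative; its first row, for example, is "LY 7 U LY 15 U H 30 U LY 30 U H 15 U H 7 U". Reading all six rows as LY (LY900014) or H (Humalog):

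| Sequence | Doses 1–2 | Doses 3–4 | Doses 5–6 |
|---|---|---|---|
| 1 | LY, LY | H, LY | H, H |
| 2 | LY, LY | LY, H | H, H |
| 3 | LY, H | LY, H | LY, H |
| 4 | H, H | LY, H | LY, LY |
| 5 | H, H | H, LY | LY, LY |
| 6 | H, LY | H, LY | H, LY |

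- Both insulins received to date: 2 of 6 sequences at Period 3 (sequences 3 and 6), and 6 of 6 at Period 5 and at follow-up.
- Both insulins received since the previous sample: 2 of 6 (doses 1–2), 6 of 6 (doses 3–4), 2 of 6 (doses 5–6).
- So 4 of 6 sequences are still single-product at Period 3, and none is afterwards.

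**Non-completers.** On the planned figures, 42 − 34 = 8 subjects, or 8/42 = 19%, might not complete. Only a subject who stops after exactly one dose gives a scheduled sample (at early discontinuation) that follows a single treatment.

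**The case against.** Four points can be made for the plan.

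1. *The SAP also uses treatment to mean product.* The mixed model in SAP 9.3.2 has treatment and dose level as separate effects, and SAP 9.5.10 separates dose level from treatment. On that reading, Period 3 samples in 4 of the 6 example sequences can be assigned to a product. This stands as an exception, but it goes no further. Section 6 defines six treatments for the tables, and Period 5 and follow-up samples mix both products on either reading.
2. *The table shells were not available and may contain an assignment rule.* They may, and a rule would remove the ambiguity. It could not isolate one treatment in a completer, because the sampling does not.
3. *The stakes are low.* The objective is exploratory, individual listings are already planned, SAP 9.5.12 plans no inferential safety analysis, and both products contain insulin lispro, the antigen being tested. This stands and limits how much weight the point deserves.
4. *The planning numbers are soft.* Other sections describe enrolment as up to 42 and completion as approximately 34, so 8 non-completers is a planning difference and not a guaranteed ceiling. This also stands. The 0, 2, 4, 6 count does not depend on it.

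**Conclusion.** The concern holds. For completers and scheduled samples, a frequency table over the six treatments of SAP section 6 has no valid interpretation by treatment: 0 of 102 post-dose samples follow a single treatment, assuming 34 completers and full sampling. The count follows from the complete crossover and the sampling schedule, and does not rest on the example sequences. The exceptions are early-discontinuation or adverse-event-triggered samples taken after one dose and, at product level only, Period 3 samples in single-product sequences.

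This is a stated analysis that the data cannot support, and so more than a missing detail. Its reach is one descriptive exploratory table. The SAP should be changed, but nothing else in the trial's conclusions turns on it.

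**What to change.** In SAP 9.5.9, replace the by-treatment summary with a summary by sampling time (Period 1 pre-dose as baseline, Period 3 pre-dose, Period 5 pre-dose, follow-up or early discontinuation) and overall. Count antibody formation relative to the Period 1 pre-dose sample.

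These additions would make the table easier to use but are not needed to cure the attribution problem:

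- State what counts as treatment-emergent (new positivity, a defined rise, or both) and how a missing baseline is handled.
- Show early-discontinuation samples separately, by number of doses received.
- Add sequence and treatments received to date to the individual listing, if the shells do not already have them.

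The cost is a few sentences in the SAP and matching edits to the table and listing shells. No extra blood samples are needed.

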9.5.10 C-peptide

C-peptide data will be summarized by treatment. Figures of mean and individual C-peptide concentrations versus time will be presented by dose level for both treatments. In addition, individual plots overlaying the C-peptide concentration versus time with the insulin lispro serum concentration versus time will be presented.

Sensitivity analysis removing subject(s) who could have potential confounding on the PD parameters will be performed as described in Section 9.4.2. Potential C-peptide confounding is

defined as when a substantial and implausible rise in C-peptide over baseline while the glucose infusion is ongoing.

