3.2. Background

The insulin analogue, insulin lispro (Humalog; Eli Lilly and Company), has been shown to be absorbed more quickly than regular human insulin (Humalog package insert, 2015). In healthy volunteers given subcutaneous (SC) doses of insulin lispro ranging from 0.1 to 0.4 U/kg, peak serum levels were seen 30 to 90 minutes after dosing (Humalog package insert, 2015). However, the general consensus is that rapid-acting insulin, administered either through pumps or syringes/pen injectors, is still not rapid enough to match carbohydrate absorption profiles, which limits efficacy and dosing flexibility. An ultra-rapid-acting prandial insulin would shift the PK and GD profiles so that they have an even faster onset to better match carbohydrate absorption and also may allow important flexibility in the time of dosing relative to meals.

LY900014 is an ultra-rapid-acting insulin lispro formulation with treprostinil CCI [REDACTED] and other ingredients. LY900014 has an increased early absorption of insulin lispro compared to commercially available insulin lispro (Humalog). CCI [REDACTED]

Treprostinil is a prostacyclin analogue, administered either through inhalation CCI [REDACTED], as an intravenous (IV) infusion, or as a continuous SC administration for the treatment of symptomatic pulmonary arterial hypertension (PAH) and has been approved in the US since 2002 CCI [REDACTED]. Each of the other excipients (such as sodium citrate and magnesium chloride) in the LY900014 formulation is listed in the US Food and Drug Administration (FDA)'s Generally Recognized as Safe Food Additives database and in the FDA's Inactive Ingredients in Approved Drugs database. Furthermore, the excipient concentration in LY900014 is within the limits identified for approved drug products in the FDA Inactive Ingredients in Approved Drugs database.

Safety and tolerability of LY900014 have been demonstrated in healthy subjects in 3 previous clinical studies, in approximately 71 healthy subjects across a dose range of 7.5 to 30 U. All 3 studies were Phase 1, randomised, subject-blind studies in which the PK and GD of LY900014 and Humalog were evaluated during a euglycaemic glucose clamp following SC administration. The total insulin lispro exposure and GD effect were similar for LY900014 and Humalog insulin

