5.1. Overall Design

This is a Phase 1, randomised, subject- and investigator-blind, 6-period complete crossover study in up to 42 healthy subjects to evaluate the PK and GD characteristics across a range of LY900014 doses.

Approximately 34 subjects are expected to complete the study. Each subject will be randomised to 1 of 6 treatment sequences comprising single SC doses of 7, 15, and 30 U of LY900014 or Humalog administered SC in the abdominal wall ([Table ITSH.2](#)). A minimum of 3 days between study dosing of each consecutive study period will be required for an individual subject.

[Figure ITSH.1](#) illustrates the study design.

Study governance considerations are described in detail in [Appendix 3](#).

[figure not shown]

Figure ITSH.1. Illustration of study design for I8B-MC-ITSH.

Table ITSH.2. Treatment Sequence Example for I8B-MC-ITSH

Treatment Sequence	Period 1	Period 2	Period 3	Period 4	Period 5	Period 6
1	LY 7 U	LY 15 U	H 30 U	LY 30 U	H 15 U	H 7 U
2	LY 15 U	LY 30 U	LY 7 U	H 7 U	H 30 U	H 15 U
3	LY 30 U	H 7 U	LY 15 U	H 15 U	LY 7 U	H 30 U
4	H 7 U	H 15 U	LY 30 U	H 30 U	LY 15 U	LY 7 U
5	H 15 U	H 30 U	H 7 U	LY 7 U	LY 30 U	LY 15 U
6	H 30 U	LY 7 U	H 15 U	LY 15 U	H 7 U	LY 30 U

Abbreviations: H = Humalog; LY = LY900014.

Note: This is only an example table for illustration purpose; subjects will be assigned a treatment sequence according to the actual treatment randomisation schedule provided to the unblinded site pharmacist.

Subjects will be admitted to the clinical research unit (CRU) on the evening before each dosing day and will remain in the CRU for the duration of the clamp period and until discharge by the investigator. Subjects are expected to fast for at least 8 hours before each dose. Following dose administration, each subject will undergo an euglycaemic clamp procedure of up to 10 hours. Upon completion of the clamp procedures, the subjects will be provided a meal and discharged from the CRU in the evening after medical assessments. Subjects may remain in the CRU if deemed necessary for safety monitoring, as determined by the investigator.

Subjects will be required to attend the CRU on at least 8 occasions:

- screening visit (up to 28 days prior to dosing)
- six treatment visits for the dosing and clamp procedure (study Periods 1 to 6) with a minimum period of at least 3 days between consecutive clamp visits
- follow-up visit (at least 14 days after the last dose), or early discontinuation

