6.3.1. Meals and Dietary Restrictions

For all treatment periods, subjects will fast for at least 8 hours prior to dosing and until the glucose clamp procedure is completed, after which subjects will receive a meal. Water can be consumed freely during this time.

When not a resident at the CRU, subjects will be encouraged to follow their normal diets.

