9.6. Glucodynamics (Euglycaemic Glucose Clamp)

The aim of the euglycaemic glucose clamp is to maintain target glucose levels through infusion of a 20% d-glucose (dextrose) solution after the administration of a dose of insulin. During the glucose clamp, the glucose infusion rate (GIR) will be adjusted to maintain a predetermined target blood glucose concentration for the individual subject. Thus, blood glucose concentrations are kept constant while the GIR varies. The varying GIR will then reflect the GD activity of insulin.

At least 30 minutes before the planned administration of study drug, subjects will be connected to the clamp device **CCI** for continuous blood glucose monitoring to determine their baseline blood glucose. Baseline is defined as the mean of blood glucose concentrations at approximately -6, -4, and -2 minutes (before study drug administration) as measured using **CCI**. After study drug administration, onset of action occurs when blood glucose drops 5 mg/dL (0.3 mmol/L) from baseline (as measured by **CCI**). This blood glucose level 5 mg/dL below baseline will be used as the euglycaemic glucose clamp target level throughout the remainder of the clamp procedure. Subjects will not be clamped to a blood glucose target lower than 63 mg/dL. Therefore, subjects with a mean predose baseline fasting blood glucose below 68 mg/dL (equivalent to a fasting plasma glucose of 76 mg/dL [4.21 mmol/L]) will not be dosed to undergo the clamp procedure but may be rescheduled to a later period. In addition, any study procedures conducted up to that time may be repeated in that later period.

After the onset of action has been reached, a variable IV glucose infusion will be initiated in order to keep blood glucose constant at the target level. The GIR necessary to keep the blood glucose concentration at the target level will be recorded every minute throughout the glucose

clamp. Frequently or at least every 30 minutes throughout the glucose clamp, blood glucose measurements for verification of CCI measurements will be performed using CCI.

The clamp procedure will continue for up to 10 hours after dose or until after blood glucose concentrations return to baseline without any glucose being administered for at least 30 minutes, whichever is earlier. At the end of the clamp procedure, the subject will be given a meal.

All subjects will be medically assessed before discharge from the CRU (see Schedule of Activities [Section 2]).

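### Could C-peptide samples drawn after an early clamp end and a meal distort the late by-treatment means in SAP 9.5.10?

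*SAP*

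**What the plan says.** **Sampling.** The Schedule of Activities (Protocol Section 2) sets C-peptide samples at "0, 60, 120, 240, 360, 480, and 600 minutes", counted from dosing. Protocol Appendix 5 counts 7 samples in each of 6 periods, 42 in all, with no reduction for a short clamp.

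**Clamp end.** Under Protocol 9.6 the clamp lasts up to 10 hours or "until after blood glucose concentrations return to baseline without any glucose being administered for at least 30 minutes, whichever is earlier".

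**Meal.** The same section adds: "At the end of the clamp procedure, the subject will be given a meal". Protocol 6.3.1 has subjects fast "until the glucose clamp procedure is completed, after which subjects will receive a meal", and Protocol 5.1 agrees: "Upon completion of the clamp procedures, the subjects will be provided a meal". None of these ties the meal to the 600-minute sample, and none says how soon after clamp end it is served.

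**Analysis.** SAP 9.5.10 says "C-peptide data will be summarized by treatment". It also calls for mean and individual plots by dose level with both products, and individual overlays with insulin lispro. Its only C-peptide screen concerns a "substantial and implausible rise in C-peptide over baseline while the glucose infusion is ongoing", and that screen removes subjects from a sensitivity analysis of the glucodynamic parameters.

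**Status.** C-peptide is an exploratory objective (SAP 4.3), and SAP 9.5.12 plans no inferential analysis for the group of assessments that includes it.

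**The concern.** C-peptide reflects the subject's own insulin secretion, which a meal stimulates. If a clamp stops at, say, 400 minutes and the subject then eats, the 480- and 600-minute values may be fed values. The SAP would average them with fasted values from clamps still running, and its C-peptide screen would not catch them, because an early end requires at least 30 minutes without infusion.

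The stopping rule depends on insulin action wearing off. Early ends are therefore plausibly commoner at 7 U than at 30 U, and meal status at late times could vary with dose. A reader comparing late means across dose levels might then take a meal effect for a drug effect. What is at stake is the reading of the late part of an exploratory, descriptive profile.

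**Working it through.** The plan gives no figure on this point to reproduce. The check has three parts: counting exposed samples, illustrating the size, and seeing what the other outputs reveal.

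**1. Exposed samples.** Inputs: the seven sampling times in Protocol Section 2 and the clamp-end rule in Protocol 9.6.

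| Clamp ends | Samples after clamp end | Count of 7 |
|---|---|---|
| at 600 min | none | 0 |
| between 480 and 600 min | 600 | 1 |
| between 360 and 480 min | 480, 600 | 2 |
| between 240 and 360 min | 360, 480, 600 | 3 |

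If every clamp ended between 240 and 360 minutes, 3 × 6 = 18 of a subject's 42 samples would be exposed (43%). The rule sets no earliest time, so still earlier ends are not formally excluded. Against this, Appendix 5 budgets a 10-hour clamp in every period: 11.5 hours including calibration and baseline, × 6 = 69 hours. Protocol 5.4 also rests its rationale on a 10-hour clamp. No clamp-end times are given, so the true count may be zero.

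**2. Size, under assumptions.** Let p be the share of subjects sampled after the meal at a given time point, and k the ratio of fed to clamp C-peptide. Neither is in the documents. The arithmetic mean is multiplied by 1 + p(k − 1).

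| p | k = 1.5 | k = 4 |
|---|---|---|
| 0 | 1.00 | 1.00 |
| 5% | 1.025 | 1.15 |
| 10% | 1.05 | 1.30 |
| 25% | 1.125 | 1.75 |

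Take two dose levels with no true difference, p = 25% at one and 5% at the other. The apparent ratio of means is 1.125/1.025 = 1.10 at k = 1.5 and 1.75/1.15 = 1.52 at k = 4. With equal p it is 1.00 for any k.

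**3. Which comparison is exposed.** The objective concerns C-peptide after each of the two products, and the plots set the products side by side at the same dose. No between-dose contrast is specified for C-peptide. A same-dose product comparison is distorted only if p differs by product. On that, Protocol 3.2 says of earlier studies: "The total insulin lispro exposure and GD effect were similar for LY900014 and Humalog insulin" lispro. This makes a large difference in p less likely but does not rule it out, because Protocol 10.3.2.1 also looks for reduced late exposure.

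**4. What the outputs already show.** SAP 9.1 requires the median, minimum, maximum and N beside the mean. Even if every fed value exceeds every fasted one, the reported median is the 0.5/(1 − p) quantile of the fasted values: 0.5/0.90, the 56th percentile, at p = 10%; 0.5/0.75, the 67th, at p = 25%. Listings and individual C-peptide plots are required, so a late rise in one subject can be seen. Protocol 10.3.6 also allows plots of C-peptide against infusion rate or blood glucose.

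**5. The obvious remedy.** One could base the summaries only on samples up to each clamp's end. That drops samples taken after the clamp but before the meal, which are still fasted. It also leaves, at late times, only the clamps with longer insulin action. With 34 completers, about 34 × 0.75 = 25.5 would contribute at p = 25% and 34 × 0.95 = 32.3 at p = 5%, and the ones lost would not be random.

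**The case for a change.** The best case for a change is that the gap follows directly from the text and costs little to close. Sampling is tied to dosing, the meal is tied to clamp end, discharge waits for all procedures, and the SAP pools whatever results. The arithmetic mean is the plotted statistic, and a few high fed values can move it; individual plots show such values but do not correct the mean. One or two sentences, a filter on recorded clamp-end time and an extra display would settle it, and if no clamp ends early the two versions coincide.

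Most of this stands as a description. Nothing in Protocol 9.8.1 or 10.3.6, or in SAP 8, 9.1 or 13.2, fills the gap. The table and figure shells named in SAP Section 3 might carry a flag, but they were not available here. The step from the gap to a needed change does not stand. It requires an early end, then a meal before the next sample, then unequal frequencies between the groups compared, and the documents give no figure for any of these. The proposed restriction also selects on duration of insulin action, the same feature that would make p unequal in the first place, so it is not clearly the better main summary.

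**Conclusion.** No change to the plan follows. SAP 9.5.10 leaves unwritten how C-peptide samples after an early clamp end are handled, and late means could include fed values if any clamp stops early. This is a gap that analysts can fill sensibly: keep the summary of all values, mark samples taken after the recorded clamp end or meal, and report how many there are at each time point. SAP Section 3 already allows supplementary analyses, so a version without post-meal values can be added if the data call for it.

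The possible effect runs from none to a factor of 1.75 on a late mean, for p up to 25% and k from 1.5 to 4. Both ranges are assumptions. The output affected is exploratory and carries no test. The one analysis in which C-peptide removes subjects is limited to rises during infusion, so post-meal values cannot trigger it. The conclusion would be weaker if early ends proved frequent and clearly unequal between the two products at the same dose. The documents neither show nor exclude that.
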